10.7 Analysis Sets

The primary analysis of safety and effectiveness endpoints will be performed on the Full Analysis Set, defined as all subjects who are enrolled in the study and receive ablation. A Per Protocol analysis set will be defined as all subjects who have undergone the ablation procedure

and have no major protocol deviations. Effectiveness analyses will be repeated for the Per Protocol Set.

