10.8 Sample Size Justification

10.9 Analyses to be Conducted

Analyses described below will be performed on all enrolled and ablated subjects.

Disposition of Study Subjects

Subject disposition will be summarized using counts and percentages. The number and percentage of subjects completed and discontinued along with the specific reasons for discontinuation will be tabulated by ablation group and in total.

Demographic and Baseline Characteristics

Summary statistics will be provided for subject demographics and pre-operative ablation characteristics.

Primary and Secondary Endpoint Analyses

The number and percentage of tumors achieving Technique Efficacy will be summarized and a 95% confidence interval will be estimated. Hypothesis testing for the primary endpoint will be performed using the methodology described in the previous section. The number and percentage of tumors achieving Technical Success will also be summarized, and a 95% confidence interval will be estimated. Local Tumor Progression will be summarized in a similar manner. Only target lesions will be included in the primary endpoint analysis for Technique Efficacy and primary summaries of Technical Success and local Tumor Progression. Data collected on non-target tumors for these endpoints will be summarized separately and not included as part of the primary analysis. The analysis of target tumors for these three endpoints will also include a subject level summary that will be secondary or supportive to the tumor level analysis.

Summary statistics will be provided for other secondary endpoints, as appropriate, for continuous or categorical variables. Local Tumor Progression Free Survival, Progression Free Survival, and Overall Survival will be estimated using the Kaplan-Meier method and confidence intervals will be provided.

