## 6 Analysis Sets

Intent-to-treat Set (ITT) is defined as all enrolled patients with the FLEX MC ablation procedure attempted (i.e., microwave ablation initiated). The primary analysis of effectiveness endpoints and safety will be performed on the ITT. If more than 7 patients (5%) start the ablation but fail to complete ablation due to any reasons, all the secondary efficacy analyses will also be repeated under ITT set.

Full Analysis Set (FAS) is defined as all subjects who are enrolled in the study and successfully complete the FLEX MC ablation procedure. This will be used for effectiveness endpoints.

Per Protocol analysis Set is defined as all subjects who complete the FLEX MC ablation procedure and have no major protocol deviations. Primary endpoint and Technical Success analyses will be repeated for the Per Protocol Set.

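### SAP 6 narrows the Full Analysis Set to completers and contradicts itself on the set for secondary effectiveness, which can inflate Technical Success by removing stopped ablations

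*SAP*

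**What the plan says.** Protocol 10.7 places the primary analysis of safety and effectiveness on a Full Analysis Set "defined as all subjects who are enrolled in the study and receive ablation". Protocol 10.9 agrees: "Analyses described below will be performed on all enrolled and ablated subjects". Neither section asks that the ablation be completed.

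SAP 6 defines three sets.

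- **ITT:** enrolled subjects in whom microwave ablation was started. "The primary analysis of effectiveness endpoints and safety will be performed on the ITT". A conditional sentence follows: "If more than 7 patients (5%) start the ablation but fail to complete ablation due to any reasons", then "all the secondary efficacy analyses will also be repeated under ITT set".
- **FAS:** "Full Analysis Set (FAS) is defined as all subjects who are enrolled in the study and successfully complete the FLEX MC ablation procedure". Its use is given as "This will be used for effectiveness endpoints", without saying whether primary, secondary or both.
- **Per Protocol:** completers with no major protocol deviation. The primary endpoint and Technical Success are repeated on it.

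The SAP does not say what counts as successful completion.

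**The concern.** Two documents use one name for two populations, and the SAP's version selects subjects on something that happens after treatment begins. Stopping is foreseen: Protocol 5.4 lists intra-operative stopping criteria, and Protocol 6.1 covers bleeding during navigation or ablation.

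For Technical Success the selection is close to the outcome itself. Protocol 6.1 grades an incomplete tumor ablation as A2, which is a failure. An ablation stopped after energy delivery starts is a likely A2, and dropping it because it was not completed removes a likely failure from the denominator. The Per Protocol repeat does not bring it back, because that set also requires completion. If successful completion were taken to mean an A0 or A1 result, Technical Success on the FAS would be 100% by construction.

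At stake is whether the reported secondary effectiveness results describe everyone in whom ablation was started, as the protocol intends, or only those in whom it went to plan.

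**Working it through.** **1. The plan's own figures.** Inputs from SAP 7: goal 0.80, assumed rate 0.90, one-sided 0.025, power above 90%, 5% dropout.

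- n = [(1.960·√(0.8·0.2) + 1.282·√(0.9·0.1)) / 0.10]² = 136.5, rounded up to 137; power at 137 is 90.1%.
- 137/0.95 = 144.2, rounded up to 145.
- 5% of 145 = 7.25, so the trigger of more than 7 matches 5% at full enrollment: 7/145 = 4.8% gives no repeat, 8/145 = 5.5% gives one.

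**2. Which set is the default for secondary endpoints?** If the ITT sentence covered every effectiveness endpoint, the secondary analyses would already be on ITT, and a rule that they are also repeated there above a threshold would do nothing. The rule has an effect only if their default is the FAS. On that reading:

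- 1 to 7 non-completers: secondary effectiveness on completers only, with no ITT repeat;
- 8 or more: the non-completers are still outside the FAS, but an ITT repeat is added.

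**3. Size for Technical Success.** Assumptions: N = 145 started, one target tumor each, k non-completers, all counted as failures. With x successes, the gap is x/(N−k) − x/N = (FAS rate) × k/N.

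| k | Successes | FAS | ITT | Gap (points) |
|---|---|---|---|---|
| 7 | 124 | 124/138 = 89.9% | 124/145 = 85.5% | 4.3 |
| 7 | 131 | 131/138 = 94.9% | 131/145 = 90.3% | 4.6 |
| 7 | 138 | 138/138 = 100% | 138/145 = 95.2% | 4.8 |
| 3 | 128 to 142 | 90.1% to 100% | 88.3% to 97.9% | 1.9 to 2.1 |
| 1 | 130 to 144 | 90.3% to 100% | 89.7% to 99.3% | 0.6 to 0.7 |

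**4. Month-12 time-to-event endpoints.** Assumption: no censoring, 7 non-completers. If all 7 have the event, the ITT value is S·138/145. If none does, it is (S·138 + 7)/145. The 58% row uses the 1-year PFS that Protocol 3.0 reports for image-guided thermal ablation; the other rows are illustrative.

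| S on FAS | All 7 have the event | None has the event |
|---|---|---|
| 58% | 55.2% | 60.0% |
| 80% | 76.1% | 81.0% |
| 90% | 85.7% | 90.5% |

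If the 7 fare like the rest, the change is about zero. The sign is therefore open.

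**5. The trigger at smaller N.** Protocol 5.1 and SAP 1 allow enrollment to stop before 145. Since 7/0.05 = 140, below 140 ablated subjects 7 non-completers exceed 5% without triggering a repeat. At the 130 used in the SAP 8.8.1 tipping-point example, 7/130 = 5.4%.

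**The case against.** The strongest reply is the ITT sentence itself. It speaks of effectiveness endpoints in the plural and does not restrict them to Technique Efficacy, so one can argue that ITT is already the main set throughout. This stands to the extent that exclusion from the secondary results is the more coherent reading of contradictory text, not an established fact. It does not remove the need for a correction, because on this reading the conditional repeat has no function and the protocol and SAP definitions still differ.

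A reader might infer that every secondary effectiveness estimate is biased toward the device. The documents do not support that. Subjects in whom ablation started have normally had navigation confirmed by CBCT, so removing them cannot raise Navigational Success. For LTPFS, PFS, DSS and OS the effect depends on outcomes the documents do not give, and the same is true of lung function and quality of life.

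A reader might also infer that stopped subjects, including any who die, vanish from the report. They do not. Safety is on ITT, SAEs are captured to study end, the DSMB reviews all deaths, and SAP 8.2 tabulates the number in each analysis set.

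Three further limits stand:

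- A completed procedure can still be read A2, and that result stays in the FAS unless successful completion means A0 or A1.
- Protocol 5.4 lets some stopped procedures be re-attempted, and those later completed could enter the FAS.
- Technical Success is summarized mainly by tumor, with up to two targets per subject, so subject denominators are illustrative.

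**Conclusion.** The point holds, with moderate confidence. The conflict between Protocol 10.7 and SAP 6 over the Full Analysis Set is plain, and SAP 6 contradicts itself on the set for secondary effectiveness. On the reading that gives the trigger a purpose, up to 7 subjects can be left out of those results with no ITT version produced.

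Only Technical Success has a clear direction: upward, by about 4.3 to 4.8 points with 7 non-completers and 0.6 to 0.7 with one, at FAS rates of 90% to 100%. These figures assume 145 started, one target tumor each, and failure in every non-completer. Seven is the maximum below the trigger, and no document gives an expected rate of stops after energy delivery begins, so the upper figure is a worst case below the trigger.

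The primary Technique Efficacy test is assigned to ITT on either reading, so the comparison with 0.80 and the sample size are unaffected, as is safety. SAP 5 plans no hypothesis tests on secondary endpoints, so the issue is the accuracy of the estimates and not error control.

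**What to change.** In SAP 6:

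1. Make the ITT set (microwave ablation initiated) the main set for all secondary effectiveness endpoints, without condition. This is in line with the Protocol 10.7 FAS. One sentence should say that receiving ablation means energy was started, since Protocol 5.6 elsewhere equates initiation of the procedure with the start of navigation.
2. Delete the trigger based on 7 non-completers.
3. Count an ablation that was started but stopped as not achieving Technical Success unless the post-ablation CBCT is read A0 or A1.
4. Keep completers as a supportive set under a different name, and define successful completion.

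The cost is SAP wording only; no new data are needed. Secondary rates may come out slightly less favourable.

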## 7 Sample Size Justification

Establishment of the performance goal for Technique Efficacy was determined through performing a systematic literature review and meta-analysis to obtain a pooled estimate for MWA and RFA based on available published literature. Ovid MEDLINE®, Embase, and Evidence Based Medicine Reviews from January 1, 2005 to March 31, 2021 were searched to identify literature reporting on studies that included at least 20 adult subjects with NSCLC or lung metastases who were treated with MWA or RFA and reported on Technique Efficacy at a target of one-month post-ablation (up to a maximum of 3 months). Study designs included randomized controlled trials, comparative observational studies, and single-arm studies. Conference abstracts, studies with less than 20 subjects, and studies assessing salvage therapies were excluded.

A total of 19 studies of percutaneous ablation were included with random-effects and fixed-effects methodologies being applied to obtain a point estimate of average Technique Efficacy and corresponding 95% confidence interval.

Results from the representative set of MWA studies demonstrated a point estimate of average Technique Efficacy to be 89% with 95% confidence interval (81%, 94%). In consideration of the lower bound of the estimated confidence and a clinically meaningful minimum acceptable level of performance while recognizing that there may be some learning curve with the new technology and allowing for a modest region of indifference, a performance goal of 80% was established for this study.

Determination of the study sample size was then performed based on a power analysis where the null hypothesis being considered was  $H_0: p \leq 0.80$  against the alternative hypothesis of  $H_1: p > 0.80$ , where  $p$  represents the true 30-day Technique Efficacy rate of FLEX MC and 0.80 is the performance goal. It is assumed that the expected Technique Efficacy rate observed for FLEX MC will be 0.90 and, therefore, a sample size of 137 subjects will provide greater than 90% power for evaluating the above hypotheses at a one-sided significance level of 0.025 using the Normal approximation to the Binomial distribution. Accounting for up to 5% dropout at the 30-day timepoint leads to a sample size of 145 subjects. This conservatively assumes one target tumor per subject.

At least 50% of the study population will be enrolled from sites in the United States.

## **8 Analyses to be Conducted**

### **8.1 General Conventions**

Simple descriptive statistics, such as mean, median, standard deviation, interquartile range, maximum, and minimum for continuous variables, and counts and percentages for discrete variables will be used to summarize most data. In addition, subject listings will also be used to present the data.

All results will be presented overall and by region to assess similarity of clinical results. For the primary and selected secondary endpoints, summary will also be presented by site.

### **8.2 Disposition of Study Subjects**

Subject disposition will be summarized using counts and percentages. The number and percentage of subjects in each analysis set and the number and percentage of subjects completed and discontinued, along with the specific reasons for discontinuation, will be tabulated by region (US and OUS) and in total.

A listing of subjects who discontinued study participation will be provided.

### **8.3 Demographic and Baseline Characteristics**

Demographic and baseline characteristic variables will be summarized descriptively. Demographic characteristics include age, gender, race, and ethnicity. Baseline characteristics to be summarized include:

- Smoking history

- BMI
- Key vitals (blood pressure, heart rate, and pulse oximetry)
- ECOG performance status
- Numeric pain rating scale
- EORTC QLQ-C30, QLQ-LC13
- CBC (complete blood count) with differential
- Coagulation tests – APTT and PT/INR
- Pulmonary function tests (PFTs) - Spirometry (e.g., FEV1, FVC, FEV1/FVC, FEF25-75, Peak Expiratory Flow, and Maximum Ventilation Volume), Diffusion Capacity (DLCO), Total Lung Capacity (TLC), Functional Residual Capacity (FRC), and Residual Volume (RV)
- Primary cancer diagnosis: sarcoma, renal or colorectal histology, stage, years since diagnosis, treatment for the primary cancer
- Pre-ablation lung tumor characteristics - number of tumors, target/non-target, location, size (average of long and short), distance from pleura

Ablation procedure related information will be listed.

#### 8.4 Medical History

Targeted medical history (chronic obstructive pulmonary disease/emphysema, coronary artery disease/prior myocardial infarction, congestive heart failure, hypertension, pulmonary hypertension, diabetes, chronic renal insufficiency, liver cirrhosis, and other) will be summarized with counts and percentages.

Surgical/procedural history (lung related, primary tumor related, other) will be summarized.

#### 8.5 Protocol Deviations

Protocol deviations will be assessed. Deviations that may impact the study inferences will be regarded major. Such deviations will be identified before final database lock.

The incidence of major protocol deviations, together with the corresponding deviation terms will be summarized. A listing of all major protocol deviations including subject ID, type of deviation, and reason will be provided.

## 8.6 Concomitant Medications and Procedures

Concomitant medications will be summarized and listed, as appropriate. Medications of interest (chemotherapies, immunotherapies, targeted therapies, anti-angiogenic therapies, other anti-cancer therapies or investigational agents) will also be summarized.

Concomitant procedural indications (prophylactic, adverse event, disease progression) will be summarized.

## 8.7 Product Complaints

Product-related complaints will be summarized by event timing (pre, intra, post procedure), device relation (Auris, NeuWave, both Auris/NeuWave, or Unknown), and AE association.

## 8.8 Primary and Secondary Endpoint(s) and Associated Hypotheses

### 8.8.1 Primary Endpoint(s) and associated hypotheses

Technique Efficacy is defined as the proportion of subjects with ablation of the target tumor(s) with the ablation zone completely overlapping or encompassing the entire target tumor(s) using CT imaging at 30 days (-7 to +14 days) post the original ablation procedure. If >1 target tumor, both tumors have to meet TE in order to consider TE for the subject.

The number and percentage of tumors achieving Technique Efficacy will be summarized and a 95% confidence interval will be estimated with the Wilson score confidence intervals as shown below. Hypothesis testing for the primary endpoint will be performed using the methodology described in the Section 5.

$$\left( \frac{\hat{p} + \frac{z_{\alpha/2}^2}{2n} - z_{\alpha/2} \sqrt{\frac{\hat{p}}{n} + \frac{z_{\alpha/2}^2}{4n^2}}}{1 + \frac{z_{\alpha/2}^2}{n}}, \frac{\hat{p} + \frac{z_{\alpha/2}^2}{2n} + z_{\alpha/2} \sqrt{\frac{\hat{p}}{n} + \frac{z_{\alpha/2}^2}{4n^2}}}{1 + \frac{z_{\alpha/2}^2}{n}} \right)$$

Technique Efficacy (TE) at Visit 3 (30 days post-ablation) will be performed on observed data only and involving only target lesions. The TE rate is the number of subjects achieving TE divided by the number of subjects completing Visit 3.

To assess the robustness of the conclusion based on observed data for the primary endpoint, sensitivity analyses imputing missing data is proposed as the following:

1. Worst-case analysis: All subjects not completing Visit 3 will be assumed to have not achieved TE.
2. Best-case analysis: All subjects not completing Visit 3 will be assumed to have achieved TE.
3. Tipping point analysis: All missing data will be imputed with either having achieved TE or not achieved TE, i.e., the denominator of the TE rate is based on the analysis set. By adding one TE event at each time, the p-value is calculated (worst-case to best-case). The tipping point is when the p-value is changed from ( $\geq 0.05$  to  $< 0.05$ ). After such a tipping point is determined, clinical judgment can be applied as to the plausibility of the assumptions underlying this tipping point (essentially, if we have 145 ITT patients, tipping point is 126 TE events; if we have 130 ITT patients, tipping point is 113 TE events).

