## **5 Levels of Significance**

The following hypotheses will be evaluated in this study:

$$H_0: p \leq 0.80 \text{ vs.}$$

$$H_1: p > 0.8$$

where  $p$  represents the true 30-day Technique Efficacy rate of FLEX MC and 0.80 is the performance goal, which was determined through an internal systematic literature review and meta-analysis of microwave and radiofrequency ablation systems used in the treatment of lung tumors.

A one-sided significance level of 0.025 will be used to test the hypotheses above. If the lower bound of the confidence interval is above 0.8, then the following secondary endpoints will be provided with 95% confidence intervals at month 12, in addition to the descriptive statistics:

- Local Tumor Progression Free Survival,
- Progression Free Survival,
- Disease Specific Survival, and
- Overall Survival

No other formal hypothesis tests are planned for this study and estimation for all other endpoints will be provided descriptively.

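### The single confirmatory test has two units of analysis, tumor in the Protocol and subject in the SAP, so the same data can pass or fail, and the one-tumor power assumption is not conservative

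*SAP*

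**What the plan says.** **Protocol.** Section 10.9 reports TE as a number and percentage of tumors with a 95% confidence interval, and the Protocol Summary does the same. For target tumors, 10.9 adds "a subject level summary that will be secondary or supportive to the tumor level analysis". The missing-data paragraph of the same section, however, counts subjects.

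**SAP 8.8.1.** TE is defined as a proportion of subjects, with the rule "If >1 target tumor, both tumors have to meet TE in order to consider TE for the subject". The denominator is explicit: "The TE rate is the number of subjects achieving TE divided by the number of subjects completing Visit 3". The tipping points (126 of 145, 113 of 130) count patients. Yet the interval sentence reads "The number and percentage of tumors achieving Technique Efficacy will be summarized and a 95% confidence interval will be estimated", using the Wilson method. SAP 8.8.2 also treats the subject-level result as an addition to the tumor-level analysis.

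**SAP 5.** "A one-sided significance level of 0.025 will be used to test the hypotheses above", and "0.80 is the performance goal". The follow-on step is conditioned by "If the lower bound of the confidence interval is above 0.8", without saying whether that interval is for tumors or subjects.

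**SAP 7.** An assumed TE rate of 0.90 gives 137 subjects for more than 90% power, and 145 after 5% dropout. The paragraph adds: "This conservatively assumes one target tumor per subject". Both documents allow up to two target tumors per subject.

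**The concern.** What the Protocol ranks as supportive is the primary definition in the SAP, so the SAP is not simply adding detail. If some subjects have two target tumors, the two definitions have different numerators, denominators and pass marks. The study is open-label, and the analysis after Visit 3 is meant to support regulatory filing. An unsettled unit leaves room to choose it once the results are known.

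Each reading also has its own fault:

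- **Subject level, both tumors required.** A two-tumor subject succeeds less often than a one-tumor subject. Assuming one tumor each then overstates the power.
- **Tumor level.** Two tumors in one subject share the patient, the operator and the session. A plain Wilson interval treats them as independent and can be too narrow.

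**Working it through.** **Inputs.** From SAP 5 and 7: p0 = 0.80, p1 = 0.90, one-sided alpha 0.025, 137 evaluable subjects, 145 after dropout. From SAP 1: at most two target tumors per subject. Assumed, because the documents do not give them: the share f of subjects with two target tumors, and the within-subject correlation ρ.

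**1. The plan's own figure.** n = [1.960·√(0.8·0.2) + 1.282·√(0.9·0.1)]² / 0.10² = 136.5, so 137. Normal-approximation power at 137 is 90.1%, and 137/0.95 gives 145. The figure reproduces for one tumor per subject.

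**2. Pass marks.** The smallest counts for which the Wilson 95% lower bound exceeds 0.80 are 113/130, 119/137, 126/145 and 142/164. The first and third equal the SAP's tipping points. The standard Wilson formula was used; the formula in the available text lacks the (1 − p̂) factor, which may be an extraction fault. With one tumor each, the 119/137 rule has exact alpha 2.45% and exact power 91.0%.

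**3. Opposite verdicts.** Take 137 subjects, 27 with two tumors, so 137 + 27 = 164 tumors. Let 20 tumors fail, in 20 different subjects.

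| Unit | Result | Wilson 95% interval | Needed | Verdict |
|---|---|---|---|---|
| Tumor | 144/164 = 87.8% | 81.9% to 92.0% | 142 | pass |
| Subject | 117/137 = 85.4% | 78.5% to 90.3% | 119 | fail |

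The subject rule tolerates 137 − 119 = 18 failures and the tumor rule 164 − 142 = 22. With at most one failed tumor per subject, any count from 19 to 22 splits the verdict. In simulation at a per-tumor rate of 0.90 with 27 two-tumor subjects, the rules disagree in about 20% of trials if outcomes are independent and about 9% at ρ = 0.5. Nearly all of these are a tumor-level pass with a subject-level fail.

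**4. Power under the both-tumors rule.** For a two-tumor subject, P(both succeed) = 0.9² + ρ·0.9·0.1 = 0.81 + 0.09ρ. The subject rate is 0.9(1 − f) + f(0.81 + 0.09ρ). For f = 20% and ρ = 0 this is 0.72 + 0.162 = 0.882. Exact power is P(X ≥ 119) for 137 subjects at that rate. The last column is the evaluable number that restores 90% power by the plan's own formula.

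| f | ρ | Subject rate | Exact power, n = 137 | n for 90% power |
|---|---|---|---|---|
| 0 | any | 0.900 | 91% | 137 |
| 10% | 0 | 0.891 | 84% | 170 |
| 10% | 0.5 | 0.8955 | 88% | 152 |
| 20% | 0 | 0.882 | 74% | 214 |
| 20% | 0.5 | 0.891 | 84% | 170 |
| 30% | 0 | 0.873 | 62% | 276 |
| 30% | 0.5 | 0.8865 | 79% | 190 |

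By the plan's normal approximation the powers are somewhat lower: 82%, 71% and 58% at ρ = 0. Retaining all 145 subjects barely changes the exact values (84%, 74%, 62% at ρ = 0). Even f = 5% gives 88% (ρ = 0) or 89% (ρ = 0.5).

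**5. Tumor-level reading.** Here extra tumors raise power: at ρ = 0 and 0.5 it is 94% and 92% for f = 20%, and 97% and 95% for f = 30%. One-sided error of the plain Wilson rule at a per-tumor rate of 0.80, 137 subjects:

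| Two-tumor subjects | ρ = 0 | ρ = 0.5 | ρ = 0.8 |
|---|---|---|---|
| 14 (10%) | 2.0% | 2.5% | 2.8% |
| 27 (20%) | 1.9% | 2.7% | 3.2% |
| 41 (30%) | 2.6% | 3.9% | 4.8% |

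Part of the movement between rows comes from the discreteness of the pass mark.

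**The case against.** The strongest reply has four parts.

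1. **Neither document is purely one or the other, and the SAP governs detail.** The Protocol defers full analysis details to the SAP, and most of SAP 8.8.1 is by subject. This is fair and shows which way to resolve the conflict. But the Protocol describes the SAP as a supplement, and the SAP still ties its interval to tumors, so the conflict remains.
2. **The 0.90 could be the subject rate with two-tumor subjects already included.** Power would then stay at about 90%. SAP 7, however, frames the calculation as one target tumor per subject. Even on the other reading, the sentence calling that assumption conservative would have no bearing and should go.
3. **The sizes depend on assumptions.** This stands. The 62% needs a 30% share and full independence. At 10% and ρ = 0.5 the power is 88%.
4. **The type I excess is small at modest shares.** This also stands: at 10% to 20% two-tumor subjects and ρ up to 0.8 it is at most about 3.2%. Under the both-tumors rule, with a per-tumor rate of 0.80, the error falls below 2.5%; that reading threatens power, not false positives.

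It can also be said that a tumor-level primary analysis with clustering handled would reconcile the texts. That is true, but it would mean rewriting the SAP's definition, denominator and tipping points.

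**Conclusion.** The point holds. The primary endpoint has two incompatible units, between the documents and within SAP 8.8.1, and the pass/fail decision can turn on which is used. That conclusion requires only that some subjects have two target tumors, which both documents allow.

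The power conclusion also needs 0.90 to be the rate for a single tumor, as SAP 7 implies, and the both-tumors rule to apply. One tumor per subject is then the most favorable case. For two-tumor shares of 10% to 30%, exact power lies between 62% and 88% over ρ = 0 to 0.5, against the stated figure above 90%. The loss disappears only if no subject has two tumors or the paired outcomes always agree.

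Under the tumor-level reading the assumption is conservative for power, but the plain interval can let the one-sided error rise to about 4% to 5% at a 30% share with correlation 0.5 to 0.8. Because this is the study's only confirmatory test, the texts must be reconciled before the primary endpoint is analysed.

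**What to change.** - **Protocol 10.9 and Summary:** make the subject the primary unit for TE, with success requiring every target tumor to succeed, and make the tumor-level result supportive. The sample size, the TE denominator and the missing-data rules already count subjects.
- **SAP 5 and 8.8.1:** state that the Wilson interval, the test and the 0.80 comparison apply to subjects. Align the TE sentence in 8.8.2.
- **Tumor-level TE:** report it with an interval that allows for clustering by subject, such as GEE or Rao-Scott.
- **SAP 7:** delete the word claiming conservatism, say whether 0.90 is a per-tumor or a subject rate, and restate power over two-tumor shares of 0% to 30% and a range of correlations.

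The cost is wording and a less favorable stated power. No extra patients or data are needed to settle the unit. If the sponsor wishes to keep 90% power under the assumptions above, that is a separate decision; it would take 152 to 276 evaluable subjects before dropout for shares of 10% to 30%.
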